**Determination of sample size:**

The objective of this study is to assess comparable efficacy of telerehabilitation vs. in-clinic intensive arm motor rehabilitation therapy with respect to the mean  $\Delta_{FM}$  from the Baseline Visit to the 30 Day Follow Up Visit, using a non-inferiority margin of 2.05. Based on our pilot study, the mean  $\Delta_{FM}$  in the telerehabilitation group is expected to be 4.80 with SD=3.80; extension to multiple sites and enrollment of subjects at earlier time points post-stroke may be associated with larger variance, and so a SD=4.0 is assumed. Comparable efficacy will be established provided that the lower bound of the 95% confidence interval for the difference in the  $\Delta_{FM}$  between treatment groups is greater than -2.05. Assuming 80% power, the study will therefore seek to attain 30 Day Follow Up data on N=124 subjects (62 per arm). If the dropout rate is as high as 20%, then as many as 155 subjects may need to be enrolled.

**8.4 Secondary efficacy analyses:**

Two secondary endpoints examining change in motor status will be examined. Each examines treatment effects along an independent dimension, and will be analyzed as above. These are

- Within-subject change in Box & Blocks score from the Screening Visit to the 30 Day Follow Up Visit
- Within-subject change in Stroke Impact Scale-Hand Domain score from the Baseline Visit to the 30 Day Follow Up Visit

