### 8.3 Key covariates:

Key covariates to include in the data analysis model are based on established predictors in this setting: time post-stroke (number of days from stroke onset to randomization), severity of impairment (arm motor FM score at Baseline Visit), age, and enrollment site. Stroke subtype (ischemic vs. intracerebral hemorrhage) will also be included as a covariate.

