#### Non-inferiority margin:

The trial seeks to establish comparable efficacy based upon a non-inferiority margin of 2.05 (a value that is less than half the minimal clinically important difference for change in FM score) for the difference between the two treatment groups in the mean within-subject change in FM score from Baseline Visit to the 30 day Follow Up Visit. We consider a maximum of 30% smaller mean  $\Delta_{FM}$  in the telerehabilitation group (as compared to the in-clinic treatment) to be clinically acceptable to consider it to be non-inferior. Based upon preliminary data, the mean  $\Delta_{FM}$  for the telerehabilitation group is expected to be 4.80 points. Thus, if the assumed mean  $\Delta_{FM}$  is 6.85 points in the in-clinic group, a reduction up to 30% (2.05 points) to 4.80 points in the telerehabilitation group would be concluded to be comparably efficacious.

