#### Primary efficacy analysis:

The primary analysis of the  $\Delta_{FM}$  will be conducted using an analysis of covariance (ANCOVA) model, adjusting for days from stroke onset to randomization, FM score at Baseline Visit, age, and enrollment site. The lower bound of the 95% confidence interval for the difference in  $\Delta_{FM}$  between treatment groups will be used to assess comparable efficacy. If the lower bound of the 95% confidence interval for the difference in  $\Delta_{FM}$  between groups (i.e.,  $\Delta_{FM}$

for the telerehabilitation group -  $\Delta_{FM}$  for the in-clinic group) is greater than -2.05, then we would declare telerehabilitation to be non-inferior.

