**Compliance and motivation.**

- Compliance with therapy, defined as the percentage of the 36 therapy sessions for which the subject completed assigned activities for at least 40 minutes

Compliance with rehabilitation therapy will be examined across all 36 sessions. For supervised sessions, a subject will be considered compliant if at least 40 min of assigned

therapy has been completed, determined from the therapist notes for subjects in the in-clinic group and from telerehabilitation system usage data for subjects in the telerehabilitation group. For unsupervised sessions, a subject will be considered compliant if at least 40 min of assigned therapy has been completed based on self-report for the in-clinic group and by telerehabilitation system usage data for subjects in the telerehabilitation group. To determine whether compliance with therapy differs according to treatment group, ANCOVA modeling will be used to examine compliance across the 36 sessions as a function of treatment group, controlling for days from stroke onset to randomization, age, and enrollment site. Secondary analysis will examine compliance with only the supervised therapy sessions, as well as compliance with only the unsupervised sessions.

**Motivation** (assessed along two independent dimensions):

- Activity-inherent motivation, defined as the change in score on the Physical Activity Enjoyment (PACES) Scale from baseline to end of the first week of therapy
- Consequence-related motivation, defined as the score on the Optimization in Primary and Secondary Control (OPS) Scale at the Baseline Visit

Activity-inherent motivation reflects how much a subject likes or dislikes an activity itself, independent of his or her commitment to the treatment goals. To measure this, the PACES Scale will be scored three times (at the Baseline Visit, after 3 supervised sessions, and after 18 supervised sessions). Activity-inherent motivation will be defined as the change in PACES score. Primary analysis will examine the change from baseline to end of week 1, while secondary analysis will examine change from baseline to end of week 6. To determine whether activity-inherent motivation is different for in-clinic vs. telerehabilitation therapy, ANCOVA modeling will examine differential change in PACES score between the two treatment groups, controlling for days from stroke onset to randomization, PACES score at the Baseline Visit, age, and enrollment site.

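### Section 8.4 does not name each secondary motor endpoint's own baseline as a covariate and gives neither endpoint a decision limit in its own units

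*Combined protocol and SAP*

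**What the plan says.** Section 8.4 lists change in Box & Blocks (Screening to 30 Day Follow Up) and change in SIS-Hand (Baseline to 30 Day Follow Up). The only method given is "Each examines treatment effects along an independent dimension, and will be analyzed as above".

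The analysis that precedes it, under Primary efficacy analysis, is an ANCOVA of FM change "adjusting for days from stroke onset to randomization, FM score at Baseline Visit, age, and enrollment site". Its decision rule is that if the lower 95% limit "is greater than -2.05, then we would declare telerehabilitation to be non-inferior". The Non-inferiority margin paragraph defines the limit "for the difference between the two treatment groups in the mean within-subject change in FM score from Baseline Visit" and describes it as "a value that is less than half the minimal clinically important difference for change in FM score".

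Four other places bear on the point:

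- Section 8.3 includes among the key covariates "severity of impairment (arm motor FM score at Baseline Visit), age, and enrollment site", so FM serves there as the measure of severity.
- Section 8.5 names the instrument's own starting score where it writes out a change model. The PACES model controls for "PACES score at the Baseline Visit, age, and enrollment site", and the Stroke Knowledge Exam model uses the Screening exam score. Neither lists FM.
- The schedule in Section 5.3 collects Box & Blocks at Screening and SIS-Hand at Baseline.
- The opening of Section 8 refers to primary and secondary endpoints alike as ones on which comparable efficacy is tested.

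**The concern.** In the primary model, baseline FM does two jobs: it measures severity, and it is the outcome's own starting value. When the same model is carried to Box & Blocks or SIS-Hand, only the first job is still done. Section 5.2 balances randomization on time since stroke, FM and site, so chance imbalance in starting Box & Blocks or SIS-Hand is controlled only as far as FM tracks those scores. Section 8.4 itself says that the two endpoints measure separate dimensions, so FM is not an obvious substitute.

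The decision rule does not carry over either, because a limit built from FM gains has no interpretation in blocks per 60 seconds or SIS-Hand points. At stake are the precision of the only two secondary motor endpoints and the standing of any statement that the arms are comparable on them. If the type of hypothesis, the limit and the covariate are all settled after the data are in, such a statement carries little weight.

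**Working it through.** **Step 1. Reproduce the design that the limit belongs to.** Inputs from Section 8: margin 2.05, SD 4.0, 80% power, two-tailed 0.05 (0.025 on the lower limit). True difference taken as 0.

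n per arm = 2 × [SD × (z0.975 + z0.80) / margin]² = 2 × [4.0 × (1.960 + 0.842) / 2.05]² = 59.8, so 60. The noncentral t version gives 61. The plan states 62. Power at 62 per arm is 81.4% (normal) or 80.8% (t), and 124 / 0.80 = 155. The plan's figures reproduce closely, with 2.05 as an FM quantity throughout.

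**Step 2. Where 2.05 comes from.** 0.30 × 6.85 = 2.055; 6.85 − 4.80 = 2.05; 2.05 / 4.25 = 48% of the FM clinically important difference cited in Section 3. Every input is in FM points. The documents give no expected change, SD or important difference for Box & Blocks or SIS-Hand, so no own-unit margin can be derived from them.

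**Step 3. What a bare 2.05 would do on another scale.** Power = Φ(2.05 / (SD × √(2/62)) − 1.96), with 62 per arm and a true difference of 0. The SDs of change are assumed.

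| Assumed SD of change | Power against 2.05 units |
|---|---|
| 3 | 97% |
| 4 | 81% |
| 6 | 48% |
| 10 | 21% |
| 20 | 8% |

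The same number is a lenient test or a nearly impossible one depending on the scale, so it cannot be borrowed.

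**Step 4. Value of the own baseline.** Assume equal variance σ² at both visits and a baseline to follow-up correlation r. The documents do not give r.

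- Unadjusted change score: variance 2(1 − r)σ².
- ANCOVA on the own baseline: variance (1 − r²)σ².
- Ratio: (1 + r) / 2.

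| r | Unadjusted change | Own-baseline ANCOVA | Reduction |
|---|---|---|---|
| 0.5 | 1.00σ² | 0.75σ² | 25% |
| 0.7 | 0.60σ² | 0.51σ² | 15% |
| 0.9 | 0.20σ² | 0.19σ² | 5% |

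**Step 5. Allow for baseline FM already in the model.** Let c be the correlation of baseline FM with the own baseline, and assume that FM predicts the follow-up score only through that baseline. The change score adjusted for FM then has variance (1 − r)[2 − c²(1 − r)]σ². Adding the own baseline multiplies this by (1 + r) / [2 − c²(1 − r)]. At c = 0 this is (1 + r) / 2, as in Step 4. At c = 1 it is 1, so there is no gain. Under this assumption the Step 4 reductions are ceilings, and the real gain shrinks as c rises.

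**The case against.** The strongest reply is that 8.4 can be read sensibly. Every use of 2.05 in the plan is tied to FM, and 8.4 contains no margin. Referring back to the analysis above may simply mean the same ANCOVA with the analysed instrument's score put in place of FM. Section 8.5 supports that reading, since the PACES and Knowledge Exam models use their own starting scores.

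This reply stands against three stronger inferences that a reader might draw:

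- **That the plan applies 2.05 FM points to blocks or SIS-Hand points.** No sentence does so. That is one literal reading of the cross-reference.
- **That baseline FM is the wrong covariate.** Section 8.3 names it as a severity measure and Section 5.2 balances on it, so it belongs in the model.
- **That the secondary contrasts are biased.** Under randomization, leaving out a baseline score mainly costs precision. The 5% to 25% range is also measured against an unadjusted change score, which is not the plan's model.

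The reply does not remove the gap. Under substitution, the own baseline is still unnamed and there is no own-unit margin to substitute. If no non-inferiority test is intended, the plan does not say so, and the opening of Section 8 points the other way.

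**Conclusion.** The point holds as under-specification with a free improvement attached. The own baseline of each secondary motor endpoint is collected but not named in the model, and the only stated limit belongs to another scale.

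The size is modest. Under the Step 4 and Step 5 assumptions, the variance reduction is at most 25% at r = 0.5 and 5% at r = 0.9, and smaller with FM in the model. The documents give neither r nor the correlations with FM, so the actual gain cannot be computed. If FM carries information on follow-up beyond the own baseline, these figures are a guide and not a strict bound.

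That the FM limit should not carry over needs no such assumption. The documents do not support saying that the plan has set an FM limit for these endpoints, only that it has set no other. The primary FM analysis, its margin and N = 124 are untouched.

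**What to change.** In Section 8.4, replace the cross-reference with explicit wording to this effect:

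- Each endpoint is analysed by ANCOVA of its change score with the covariates stated for the primary analysis, including FM at the Baseline Visit.
- The Box & Blocks model adds the Screening Box & Blocks score. The SIS-Hand model adds the Baseline SIS-Hand score.
- The adjusted difference between arms and its 95% confidence interval are reported in the instrument's own units.
- The -2.05 limit does not apply to these endpoints. No non-inferiority verdict is drawn on either unless a margin in its own units, with a justification, is fixed before data lock.

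The cost is a text change and one more covariate per model, with no new data. Unless margins are set, the two endpoints become supportive estimates without a pass or fail result.

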**8.5 Secondary outcome measures:****Stroke education**

- Gains in stroke knowledge from Screening Visit to Post-Therapy Visit, measured as the change in percentage of questions answered correctly on the Stroke Education Exam

In order to determine whether targeted educational material significantly increases subject knowledge related to stroke, the Stroke Knowledge Exam will be administered twice, once at the Screening Visit then again at the Post-Therapy Visit. A repeated measures ANOVA will be performed to determine if the percentage of Stroke Knowledge Exam answered correctly increases significantly from the Screening Visit to the Post Therapy Visit, controlling for days from stroke onset to randomization, initial Stroke Knowledge Exam score (at the Screening Visit), age, and enrollment site. To determine if gains in stroke knowledge vary according to the method by which stroke education is delivered, analysis will be repeated adding a time X group interaction term. Weight and blood pressure will be measured during the Screening Visit as well as during the Post Therapy Visit. In order to determine whether gains in stroke knowledge are associated with improvements in stroke risk factor control, the relationship between gains in stroke knowledge (the change in percentage of questions answered correctly on the Stroke Education Exam from the Screening Visit to the Post Therapy Visit) and improvement in weight and blood pressure control (change in weight, change in systolic blood pressure, and change in diastolic blood pressure) will be examined, controlling for days from stroke onset to randomization, Stroke Knowledge Exam score at Screening Visit, age, and enrollment site, and using a Bonferroni-adjusted alpha = 0.017; again, analyses will be repeated by adding a time X group interaction term.

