### 1.2 Specific Aim 2. Secondary Outcomes--Stroke Education and Prevention:

Many patients with stroke know little about the causes of their condition and consequently have poor control of stroke-related risk factors. Improving patient knowledge about stroke can therefore help to prevent stroke recurrence and to optimize patient outcomes. While all certified stroke centers include patient education as a priority during the acute stroke admission, patients and their families may not be in the best position to benefit from such education at this time as compared to once they have returned to their home. Aim 2 will compare two different approaches to patient education in their impact on stroke knowledge, hypothesizing that both are effective, and are effective to an equal extent. As an extension of this issue, the degree of gains in stroke knowledge is hypothesized to be related to the extent to which patients implement appropriate lifestyle changes.

**1.2.1** Subjects, having received targeted educational material for 6 weeks, will significantly increase knowledge related to stroke prevention and stroke risk factor control, measured as the change in percentage of questions answered correctly on the Stroke Education Exam from Screening Visit to Post-Therapy Visit.

**1.2.2** The change in percentage of questions answered correctly on the Stroke Education Exam from Screening Visit to Post-Therapy Visit among subjects using the telerehabilitation system will be comparable to the change in percentage of questions answered correctly on the Stroke Education Exam among subjects using a traditional paper booklet-based method.

**B.1.3** Increased stroke knowledge will be positively correlated with improvement in weight and blood pressure control.

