**3. PRELIMINARY STUDIES**

A pilot study was completed at UC Irvine 12 subjects with chronic stroke, using entry criteria similar to the current proposal, each of whom received 28 days of home telerehabilitation targeting arm motor deficits. At baseline, age was 54±16 (mean±SD; range 26-75) yr, gender

6M/6F, time post-stroke  $7 \pm 6$  mo, and arm motor Fugl- Meyer (FM) score was  $39 \pm 12$  (range 23-56). The main results were that:

- **Compliance was excellent**
  - Subjects engaged in therapy 329 of 336 (97.9%) assigned days without dropout.
  - Verizon wireless USB modem reception was present in all patient's homes.
  - Subjects rated the experience very favorably via Likert scales.
- **Arm motor status was significantly improved**
  - Total FM score increased by  $4.8 \pm 3.8$  points ( $p=0.0015$ ).
  - Significant increases found in both proximal and distal FM subscores.
- **Gains in knowledge about stroke prevention were significant and specific to the practiced materials**
  - For questions practiced daily, scores increased 39% (22.8 to 31.7 out of 40,  $p=0.0007$ ).
- **Findings were not dependent on computer skills**
  - Computer literacy scores, measured with the Computer–Email–Web Fluency Scale, declined with age ( $r = -0.90$  to  $-0.92$ ,  $p < 0.0001$ ), as expected, but were not related to gains in arm motor control or stroke knowledge.
- **Validated remote screening for depression after stroke**
  - Telehealth scoring of PHQ-9 ( $r=0.72$ ,  $p=0.008$ ) and PHQ-2 ( $r=0.94$ ,  $p < 0.0001$ ) were validated.
- **Subjects have poor recall of their recent usage and performance statistics**
  - Subjects were regularly asked to recall their scores and usage from the prior day, and whether these had changed. Their recall was not significantly related to actual values.

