**Stroke education:**

At the start of each of the 18 unsupervised sessions, all subjects will receive 5 minutes of stroke education. The information presented corresponds to the content of the Stroke Knowledge Exam, which focuses on prevention, recognition, response, and management of stroke. Subjects assigned to in-clinic therapy will review the stroke education booklet. Subject assigned to telerehabilitation will receive this information via the telerehab system.

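### The stroke-education analysis tests an uncontrolled rise in exam score, so a significant result cannot be credited to the educational material as section 8.5 and Aim 2 imply

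*Combined protocol and SAP*

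**What the plan says.** Section 8.5, under stroke education, gives the purpose of the analysis: "In order to determine whether targeted educational material significantly increases subject knowledge related to stroke, the Stroke Knowledge Exam will be administered twice". The test follows, with Post-Therapy as the second time point: "A repeated measures ANOVA will be performed to determine if the percentage of Stroke Knowledge Exam answered correctly increases significantly from the Screening Visit". It is adjusted for days from stroke onset, Screening exam score, age and site. The arms are compared in a second step, through an interaction of time with group: "To determine if gains in stroke knowledge vary according to the method by which stroke education is delivered, analysis will be repeated adding a time".

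The stroke education text in section 5.3.3 gives the material to everyone: "At the start of each of the 18 unsupervised sessions, all subjects will receive 5 minutes of stroke education". It also ties teaching to testing: "The information presented corresponds to the content of the Stroke Knowledge Exam". Delivery differs by arm (booklet or telerehabilitation system), but no arm goes without.

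Section 1.2 introduces Aim 2 as a comparison of two approaches, "hypothesizing that both are effective, and are effective to an equal extent". Hypothesis 1.2.1 beneath it is narrower: subjects who have had the material for six weeks will show a rise in percentage correct.

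**The concern.** The stated question and the planned test have different null hypotheses. The question is whether the material raises knowledge, so its null is that the material has no effect. The time effect tests whether the mean Post-Therapy score equals the mean Screening score. The two coincide only if nothing but the material can move the score between the visits.

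The plan describes nothing that would remove other sources of change: no group without education, no untaught items, no alternate exam form. The covariates do not remove a gain that everyone shares. The time-by-group term does not help either, because a shared gain cancels from it. Ineffective material plus a common retest gain would tend to give a significant time effect and no interaction, which is also the pattern Aim 2 predicts. The analysis cannot tell the two apart, so a report following section 8.5 as worded could claim an education effect that the design does not identify.

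**Working it through.** **What each planned term estimates.** Let E1 and E2 be the effects of the material in the two arms, and g a gain from other sources common to both. Mean change is E1 + g in one arm and E2 + g in the other.
- Pooled time effect (equal arms): (E1 + E2)/2 + g, so g enters in full.
- Time-by-group term: (E1 + g) − (E2 + g) = E1 − E2, so g cancels.

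With E1 = E2 = 0 and g > 0, the time effect is positive and the interaction is zero.

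**Inputs from the documents.**
- Pilot (section 3): "For questions practiced daily, scores increased 39% (22.8 to 31.7 out of 40", with p=0.0007 in 12 subjects.
- Section 8: two-sided alpha 0.05; 124 subjects (62 per arm) sought with 30 Day Follow Up data.

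**The plan's own figures.** Pilot gain: 31.7 − 22.8 = 8.9 items; 8.9/22.8 = 39.0%, as stated; 8.9/40 = 22.25 percentage points. Enrolment: 124/0.80 = 155, as stated. The documents give no power or detectable difference for the knowledge exam.

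**Assumptions.** The pilot p value came from a paired t test. The SD of change in this trial is similar (range shown: 10 to 20 points). All 124 subjects have both exams. A one-sample t test of change stands in for the covariate-adjusted model. The gain g is hypothetical throughout.

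**SD of change.** Two-sided p=0.0007 on 11 df gives t = 4.65. SD = 8.9 × √12 / 4.65 = 6.62 items, and 6.62/40 = 16.6 points.

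**Smallest significant rise.** SE = 16.6/√124 = 1.49 points. The critical t on 123 df is 1.98, so 1.98 × 1.49 ≈ 2.9 points, or about 1.2 items of 40.

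**Chance of a significant time effect when the material does nothing** (noncentral t with noncentrality g√124/SD):

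| g (points) | SD 10 | SD 16.6 | SD 20 |
|---|---|---|---|
| 1 | 20% | 10% | 9% |
| 2.5 (one item in 40) | 79% | 39% | 28% |
| 5 | >99% | 92% | 79% |

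A simulation of 20,000 trials at SD 16.6 gave 39% at 2.5 points and 91% at 5 points. The time-by-group test stayed at 5% at every gain tried. (The 39% here and the pilot's 39% relative gain are unrelated.)

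**The case against.** The strongest defence is that hypothesis 1.2.1 and its test do match. It is worded as a within-subject change over a period in which material was received, and the ANOVA tests that change. This stands. The mismatch lies in the opening clause of section 8.5 and in the word for effectiveness in the Aim 2 paragraph, and 1.2.1 needs little change.

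Second, the pilot points away from large drift. It reports: "Gains in knowledge about stroke prevention were significant and specific to the practiced materials". That implies some contrast with unpracticed material, and its gain was about 22 points. This also stands, with the limits of 12 subjects and an undescribed contrast. It makes a wholly spurious result less likely, but it does not supply the comparison in this trial.

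Third, the rival explanations are not documented in size. The exams fall roughly six to thirteen weeks apart. Montreal Cognitive Assessment scores below 22 are excluded (waivable for aphasia), which limits the room for cognitive recovery. Nothing says that outside therapy includes stroke education, that answers are given after the Screening exam, or that the items are identical at both visits. The table therefore shows what a given drift would do, not that drift will occur; any uncontrolled before-after test of this size is similarly sensitive.

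A reader might infer that the education aim will produce a false positive, or that the trial must add untaught control items. The documents support neither. The first needs a retest gain that they do not give. The second is a debatable trade-off, taken up under the fix.

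**Conclusion.** The point holds as a limit on interpretation. Because every subject receives the material, a significant pooled time effect, with or without an interaction, cannot be attributed to it. This follows from the design and needs no numerical assumption. The illustration (about 39% at a 2.5-point gain, 28% to 79% over SDs of 20 to 10) rests on a back-calculated SD and a hypothetical gain. If the trial sees a rise near the pilot's 22 points, retest alone is an unlikely full explanation; the share due to the material would still be unknown.

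Severity is minor. One part of a secondary aim is affected. A gain common to both arms cancels from the between-arm comparison in 1.2.2, and the primary Fugl-Meyer analysis is untouched.

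**What to change.** In section 8.5 and the Aim 2 paragraph of section 1.2, replace the causal purpose with a descriptive one: a significant time effect shows that stroke knowledge scores rose during the study in both arms combined, and does not by itself show that the material caused the rise. State that the between-arm comparison (1.2.2) is the only randomized inference about education, and that it compares delivery methods rather than education with none. This costs only wording; no visit, exam or model changes.

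Optionally, untaught items could be added at both visits and the change on taught minus untaught items tested. That needs equal non-education drift on both item types and no spill-over from taught to untaught content (spill-over would bias the contrast against the material), and the new items would be unvalidated. It also needs enough items. Suppose 57% correct (22.8/40), independent binomial noise and a taught-item SD of 16.6. Five untaught items give a contrast SD of √(2 × 0.57 × 0.43/5 × 100² + 16.6²) ≈ 35 points and about 88% power for a 10-point difference at N=124; four items give about 81%. The wording change does not depend on this option.

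### Aim 2 hypothesises that both education methods are effective, but section 8.5 tests only the pooled gain and the difference in gains, never the gain within each arm

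*Combined protocol and SAP*

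**What the plan says.** Section 1.2 introduces Aim 2 as a comparison of two education methods, "hypothesizing that both are effective, and are effective to an equal extent". Two numbered sub-hypotheses on knowledge follow. Number 1.2.1 is worded for the whole sample: "Subjects, having received targeted educational material for 6 weeks, will significantly increase knowledge related to stroke prevention and stroke risk factor control". Number 1.2.2 says that the gain will be comparable between the two methods.

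The methods coincide with the treatment arms. Under the stroke education heading of section 5.3.3: "Subjects assigned to in-clinic therapy will review the stroke education booklet", and "Subject assigned to telerehabilitation will receive this information via the telerehab system".

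Section 8.5 gives the analysis. First: "A repeated measures ANOVA will be performed to determine if the percentage of Stroke Knowledge Exam answered correctly increases significantly from the Screening Visit" (up to Post-Therapy). The covariates are given as follows: "controlling for days from stroke onset to randomization, initial Stroke Knowledge Exam score (at the Screening Visit), age, and enrollment site". Treatment group is not among these terms. Then, to see whether gains depend on the delivery method, "analysis will be repeated adding a time X group interaction term". No gain within an arm, simple effect or arm-specific contrast is specified. The opening of section 8 sets all analyses at two-sided 0.05.

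**The concern.** A claim that both methods work is a claim about two quantities, the gain with the booklet and the gain with the telerehabilitation system. The pooled time effect concerns their average, and the average can be clearly above zero when one of the two is zero. The interaction concerns their difference. If it is significant, the gains differ, but it remains unknown whether the weaker method works. If it is not significant, that does not show that both work.

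At stake is what can be reported for Aim 2. A significant increase overall with no significant difference between methods would probably be summarised as support for both, although neither result shows it. The method without an effect could be either one, including the education module of the system under evaluation.

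**Working it through.** **The plan's own figure.** No sample size or power is stated for stroke education. The number of subjects comes from the primary endpoint: margin 2.05, SD 4.0, 80% power, 62 per arm (section 8, Determination of sample size). With one-sided alpha 0.025 and a true difference of zero, the normal formula gives 60 per arm and the t-based version 61. Power at 62 per arm is 81%. So 62 per arm is reproduced to within two subjects and is used below.

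**Effect size from the pilot.** Section 3 reports a rise from 22.8 to 31.7 out of 40 on questions practised daily, p=0.0007, in 12 subjects who all received telerehabilitation. No SD of the change is given. I assume that the p-value comes from a paired t-test:

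- t on 11 df for two-sided p=0.0007 is 4.65.
- Gain = 31.7 − 22.8 = 8.9 of 40 = 22.25 percentage points.
- SD of change = 8.9 × √12 / 4.65 = 6.6 of 40 = 16.6 percentage points.
- Standardised gain = 22.25 / 16.6 = 1.34 SD.

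Because this SD is an assumption, the range 10 to 20 points is shown as well.

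**The two planned tests when one method has no effect.** Let the gain be d (in SDs of the change score) in one arm and 0 in the other, with 62 per arm.

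- Pooled time effect: mean d/2, standard error 1/√124, so z = (d/2)√124 = d√31 = 5.57d.
- Interaction: difference d, standard error √(2/62), so z = d/√(2/62) = d√31 = 5.57d.

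The expected z is the same for both tests. They rest on the sum and the difference of two arm means with equal variance, so they are independent. If p is the chance that either is significant, the chance that the pooled test is significant and the interaction is not is p(1 − p). This has its maximum, 25%, at p = 0.5, where d = 1.96/5.57 = 0.35. A different SD changes the gain in points at which the maximum occurs, but not its height.

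Check by simulation (40,000 runs, change scores, t-tests, no covariates):

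| d | Pooled significant | Interaction significant | Pooled significant, interaction not | p(1 − p) |
|---|---|---|---|---|
| 0.2 | 20% | 20% | 16% | 16% |
| 0.3 | 37% | 38% | 23% | 24% |
| 0.35 | 48% | 49% | 24% | 25% |
| 0.5 | 77% | 79% | 17% | 16% |
| 0.6 | 90% | 91% | 8% | 8% |
| 0.8 | 99% | 99% | 0.6% | 0.6% |
| 1.35 | 100% | 100% | 0% | 0% |

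In percentage points, a separate simulation (20,000 runs per case) gave this probability for true gains of 4, 6 and 8 points in the working arm: 20%, 25% and 18% at SD 16.6; 24%, 8% and 0.6% at SD 10; 15%, 23% and 24% at SD 20.

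**With a test in each arm.** If a significant increase is required in both arms at two-sided 0.05, a method with no effect passes in about 2.5% of trials, the upper tail. The chance of wrongly finding an increase with both is therefore about 2.5% or less at every d (simulated 0.9% at d=0.2 and 2.6% at d=0.6). Because both conditions must hold, alpha needs no adjustment.

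**Power after the change, when both methods work equally.** One arm alone has 80% power at d=0.36. Both arms together reach 80% at d=0.41 (0.41 × 16.6 = 6.8 points at the assumed SD) and 94% at d=0.5. For comparison, the pooled test has 80% power at d = (1.96 + 0.84)/√124 = 0.25.

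**The case against.** The strongest reply is that the planned tests match the numbered sub-hypotheses. Number 1.2.1 speaks of subjects overall and gets the pooled test; 1.2.2 speaks of comparable change and gets the interaction. The words about both methods being effective stand only in the introductory paragraph. This holds for 1.2.1, and the pooled test should stay. But the introductory sentence is the stated hypothesis of the aim, and nothing in section 8.5 tests it.

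A reader might infer that the plan would declare an ineffective method effective. The documents do not support that. No rule turns a significant pooled effect and a non-significant interaction into such a statement; the interaction is given only the purpose of seeing whether gains vary. What the documents show is a hypothesis without a matching test. Whether a non-significant interaction may be read as comparability belongs to 1.2.2 and is not counted here.

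The scenario is also narrow. Both arms get five minutes of education at each of 18 unsupervised sessions, five questions each time with answers explained, on the content of the exam. Nothing in the documents points to one arm having no gain at all, and at the pilot-size gain the interaction test would expose it. That stands as a limit on the size. It does not remove the gap: the pilot had 12 subjects, only telerehabilitation and daily-practised questions, and the documents report no result for the booklet.

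The simulation omits the planned covariates. Adjustment that lowers the residual SD moves the same gain to a larger d. This shifts where the risk lies, while the 25% ceiling and the missing test remain.

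Finally, the interaction model can yield arm-specific gains. That is so, and it is why the remedy is cheap, but the plan does not ask for them.

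**Conclusion.** The point holds in a limited form. Section 8.5 tests the average gain and the difference in gains, and neither can support the hypothesis that both methods are effective. If one method had no effect and the other a gain of about 0.2 to 0.6 SD, a significant pooled increase with a non-significant interaction would occur in about 8% to 25% of trials; at the pilot-size gain, in about 0%. These figures assume 62 per arm, no covariate adjustment and exactly zero gain in one arm. Their translation into points also assumes an SD of 10 to 20 percentage points. They are conditional on that scenario and are not the error rate of the trial.

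The aim is secondary. The primary endpoint, its analysis and the sample size are not affected. The change is worth making because it costs almost nothing.

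**What to change.** In section 8.5, add that the Screening to Post-Therapy gain will be estimated and tested within each arm from the time-by-group model already planned, at two-sided 0.05 with a 95% confidence interval. State that knowledge will be said to have increased with both methods only if both gains are significant; no alpha adjustment is needed. Keep the pooled time effect as the test of 1.2.1.

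The cost is a sentence or two of text and two contrasts, with no new data or subjects. There are two downsides. Power for the claim about both methods is lower than for the pooled test (80% at about 0.41 SD in each arm, against about 0.25 SD). And a within-arm gain still cannot be separated from retest effects or other changes over time, because there is no group without education. The report should say so and describe the result as an increase in knowledge with each method.
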